Cover letter

Title: Comparison Between the Dentapen and Vibraject: a Randomized Clinical Study on the Administration of Local Anaesthesia in Adult Patients.

Date: January 14, 2025

STUDY PROTOCOL

Ethical Approval

The study was conducted in compliance with the Helsinki Declaration. Each participant in this study was given a thorough explanation of the procedures and signed a consent form attesting to their comprehension. Ethical approval was obtained from the research centre at Riyadh Elm University prior to conducting this research (FPGRP/2023/715/906/892). The informed consent was obtained from the participants who volunteered in this research.

Outcome Measurement

In this study, each patient received two injections in both sides of the maxilla buccally next to the first molar, with the type of injection being randomly assigned. Immediately following each local anaesthesia injection, patients were requested to rate their pain intensity using the Visual Analogue Scale. Additionally, heart rate measurements were taken before and after each injection to monitor physiological responses to pain.

After both injections were completed, patients were asked to indicate their preferred injection. This preference was based on their subjective experience and was recorded by selecting the injection number (either the first or second) in the order they were administered for each patient. This method aimed to provide insights into patient comfort and pain perception associated

Inclusion Criteria:

- Individuals classified under American Society of Anesthesiologists classes I and II, indicating a healthy or mild systemic disease status.
- Individuals aged from 18 up to 65 years, encompassing both male and female patients.

- Individuals who required local anesthetic injections bilaterally in the buccal side of the upper posterior teeth. These injections were necessary for various dental procedures, including restorative, endodontic, or prosthodontic treatments, and volunteers as well were to be administered across both sides of upper posterior teeth.
- Individuals must be in good health, not currently taking any medication, and have no contraindications to the use of local anesthesia.
- Individuals who have the ability to understand both oral and written instructions, ensuring effective communication and comprehension throughout the study.

Exclusion Criteria:

- Individuals with allergies to local anesthetics, this is to prevent adverse reactions.

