The patient then returned after one hour, and the patient's heart rate being recorded before the administration of local anaesthesia. For this second injection, the alternative injection method was used on the other side, ensuring that each patient experienced both types of injections. Following the second injection, the patient's heart rate was measured once more to capture the immediate physiological response and the patient will be asked again to evaluate pain intensity with Visual Analogue Scale.

[figure not shown]

Figure 1: Flow chart of the study

This study design is a split mouth clinical trial which allowed for a within-subjects comparison, where each patient's reaction to both injection methods could be directly compared. The heart rate measurements before and after each injection provided objective data on the physiological response to the injections.

Steps of the Experiment

The experimental protocol was meticulously structured to evaluate the efficacy and patient response to two different local anaesthetic delivery systems. The steps were as follows:

Step I: Before administering a local anaesthetic, the patient's heart rate was checked with a pulse oximeter (Beurer Finger Pulse Oximeter). The results were recorded.

Step II: Patients were randomly assigned to get the injection of local anaesthetic at their initial appointment either with the Dentapen system (ramp-up) or with Vibraject. To simplify the protocol, a 27-gauge needle was used for all dental injections with bevel side directly headed to the injected site.

Step III: In the next appointment, after one hour on a digital timer, the other technique was used for the same patients on the other side. Hence, each patient was given local anaesthesia twice, once with the Dentapen system (ramp-up mode) and once with Vibraject.

Step IV: Immediately after each local anaesthesia injection operation, the patient was asked to use the Visual Analogue Scale to score the intensity of reported pain.

Step V: After administering a local anaesthetic, the patient's heart rate was measured with a pulse oximeter (Beurer Finger Pulse Oximeter). The results were recorded.

Step VI: After both injections were administered to each patient, they were asked which injection they would prefer by selecting the injection number (first or second) according to their order for each patient.

Risk of Bias

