Figure 2: Dentapen used in the study.

Injection with Vibraject

After drying the mucosa, a cotton-tipped applicator with a 20% benzocaine gel (Topox; Sultan Healthcare, Inc., York, PA) was placed for 60 seconds using a digital timer. After 60 seconds, the target site was wiped with another 2-inch by 2-inch cotton gauze and injecting 0.5 cartridge (0.9 mL) of 3% mepivacaine hydrochloride with no epinephrine (Henry Schein, Melville, NY) which was stored in room temperature. The needle was advanced into the tissue until it was estimated to be over the root apex while remaining parallel to the tooth's long axis. The Vibraject was activated after aspiration to deposit the solution slowly at approximately 50 seconds (time necessary to infiltrate 0.5 mL of anesthetic with the dentapen system) for both groups. The time factor was therefore limited to prevent a possible confounding effect in the patients' pain perception. Following cartridge deposition, the operator adjusted the participant to an upright

seated position so that he or she could independently record his or her perceived pain on the Visual Analogue Scale. The Vibraject was selected as the vibrator due to its simple design, battery operation, and ability to be easily attached to a syringe with minimal adjustment to conventional injection procedures. Also, compared to other vibration gadgets, it is reasonably affordable.

Figure 3: Vibraject used in the study.

Visual Analogue Scale scale

The Visual Analogue Scale score was stratified into distinct categories: "0" denoted absence of pain, scores ranging from "1-3" indicated mild pain, "4-6" signified moderate pain, "7-9" represented severe pain, and the maximum score of "10" was designated as indicative of the utmost intensity of pain conceivable.

Statistical Analysis

The statistical analysis for this study was conducted using SPSS Version 20 (IBM-SPSS Inc., Chicago, IL), a robust statistical software package that allows for detailed data management and analysis. The primary statistical tests employed were the paired T-test for analysing the heart rate data and the Wilcoxon test for the Visual Analogue Scale pain scores.

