The paired T-test was chosen for the heart rate data as it is designed to compare the means of two related groups, such as the same patients' heart rates before and after each injection. This test is particularly suitable for assessing whether there is a statistically significant change in heart rate following the administration of local anaesthesia.

For the Visual Analogue Scale pain scores, the Wilcoxon test was utilized. This non-parametric test is ideal for data that are not normally distributed and is used for comparing two related samples, matched samples, or repeated measurements on a single sample. In this study, it was employed to evaluate the differences in pain scores between the two different injection techniques on the same patients.

A p-value of 0.05 or less was considered statistically significant. This conventional threshold indicates that there is only a 5% likelihood that the observed differences occurred by chance. Thus, if the p-value is less than or equal to 0.05, the results are deemed statistically significant, suggesting a real difference between the two techniques that is not due to random variation.

RESULTS

Table 1 shows the demographic characteristics of the study population, offering insights into both age and gender distribution. The mean and standard deviation for age provides a central tendency and variability measure, while the gender distribution details the proportion of males and females in the sample. The mean age of the patients was 36.1 (SD 9.33) years, with the majority being males (87.5%).

Table 1: Descriptive statistics of study participants (N=40), highlighting age and gender distribution

Study variables	N (%)
Age in years (mean \pm SD)	36.1 \pm 9.33
Gender	
• Male	35 (87.5%)
• Female	05 (12.5%)

Figure 4 presents the study population's preferred method for injecting anaesthesia. The highest number of the participants showed interest in the Dentapen® method (n = 25, 62.5%) while 15 participants showed inclination towards the Vibraject method (37.5%).

[figure not shown]

Figure 4: Preferred method of injecting local anaesthesia by the study population

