Table 2 demonstrates descriptive statistics related to heart rate measurements, including mean, standard deviation, and standard error of the mean for different conditions. The mean heart rate before treatment is slightly lower for Dentapen® (70.225) compared to Vibraject (70.775). The mean heart rate after treatment is higher for Dentapen® (71.75) compared to Vibraject (71.05). Both Dentapen® and Vibraject showed an increase in mean heart rate after treatment.

Table 2: Heart rate before and after the procedure

		Mean	N	Std. Deviation	Std. Error Mean
Overall	Heart rate before	70.5000	80	10.16572	1.13656
	Heart rate after	71.4000	80	9.59905	1.07321
Dentapen®	Heart rate before	70.2250	40	10.04984	1.58902
	Heart rate after	71.7500	40	9.94794	1.57291
Vibraject	Heart rate before	70.7750	40	10.40091	1.64453
	Heart rate after	71.0500	40	9.35058	1.47846

Table 3 indicates a statistically significant increase in mean heart rate measurements following Dentapen® injection ($p=0.010$). However, no significant differences were observed in the mean heart rate measurements between the overall and Vibraject before and after injection ($p>0.05$).

Table 3: Comparison of mean heart rate measurements before and after injections with Dentapen® and Vibraject

	Paired Differences					t	P-value §
	Mean	Std. Deviation	Std. Error	95% Confidence Interval of the Difference			

						Lower	Upper		
Overall	Heart rate before - Heart rate after	- .90000	4.18133	.46749	-1.83051	.03051	- 1.925	0.058	
Dentapen®	Heart rate before - Heart rate after	- 1.5250	3.56613	.56386	-2.66550	-.38450	- 2.705	0.010 **	
Vibraject	Heart rate before - Heart rate after	- .27500	4.67940	.73988	-1.77155	1.22155	-.372	0.712	

§ P-value has been calculated using paired sample t-test.

** Significant at p<0.05 level.

Table 4 depicts the mean Visual Analogue Scale score. The mean score of Vibraject (2.175) was observed higher than that of Dentapen (1.550). However, the results yielded an insignificant difference (p=0.105). The overall mean Visual Analogue Scale score was 1.863.

Table 4: Comparison of Visual Analogue Scale between Dentapen® and Vibraject

	Mean	N	Std. Deviation	Std. Error Mean	P-value §
Overall	1.863	80	1.605	0.179	
Dentapen®	1.550	40	1.467	0.232	0.105
Vibraject	2.175	40	1.693	0.268	

§ P-value has been calculated using Mann Whitney Z-test.

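### Does the lack of a named analysis or interval for patient preference (25 versus 15 of 40) call for a change?

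*Combined protocol and SAP*

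**What the plan says.** Preference is a stated outcome. Under Outcome Measurement: "After both injections were completed, patients were asked to indicate their preferred injection". Step VI of Steps of the Experiment repeats it; the answer is a forced choice between the first and the second injection. The stated purpose is insight into comfort and pain perception. No hypothesis about preference is given.

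The Statistical Analysis section says: "The primary statistical tests employed were the paired T-test for analysing the heart rate data and the Wilcoxon test", the latter for the VAS scores. It names no test, estimate or interval for preference. The significance rule is general: "A p-value of 0.05 or less was considered statistically significant".

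In the Results, the text introducing Figure 4 says that "The highest number of the participants showed interest in the" Dentapen method (25 patients, 62.5%), with the other 15 (37.5%) choosing Vibraject. The text attaches no interval or p-value. Figure 4 itself is not shown in the version available for review.

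**The concern.** An outcome that patients are asked about in a dedicated step would normally have at least a one-line analysis, and here it has none. The reporting also looks uneven. Table 3 gives 95% intervals and p-values for heart rate, and the VAS result is qualified: "However, the results yielded an insignificant difference (p=0.105"). The preference split, which favours Dentapen, is stated without qualification.

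What would be at stake is the reading of the trial. With VAS labelled non-significant, someone could take the 25 to 15 split as the firmer evidence for Dentapen and not notice that 40 binary answers leave wide uncertainty. An outcome without a planned analysis also leaves the choice of method open after the data are known.

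**Working it through.** **Inputs.** N = 40 (Table 1). Preferred Dentapen 25, preferred Vibraject 15 (Results, text for Figure 4). Threshold 0.05 (Statistical Analysis). Sidedness is not stated; two-sided is assumed, to match a 95% interval.

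**1. The document's own figures.** 25 + 15 = 40, so every patient is counted. 25/40 = 62.5% and 15/40 = 37.5%. Both reproduce.

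**2. Interval for the pooled split.** Clopper-Pearson limits are beta quantiles:
- lower = Beta(0.025; 25, 16) = 0.4580
- upper = Beta(0.975; 26, 15) = 0.7727

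So 62.5% has an exact 95% interval of 45.8% to 77.3%. As a difference in shares, 2p − 1, this is 25 percentage points, from 2 × 0.4580 − 1 = −8.4 to 2 × 0.7727 − 1 = 54.5.

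**3. Test against an even split.** P(X ≥ 25 | n = 40, p = 0.5) = 0.0769; doubled, 0.154. On the same scale 26/40 gives 0.081 and 27/40 gives 0.038, so 27 is the smallest count that meets 0.05.

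**4. Does the method matter?**

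| Method | Result |
|---|---|
| Wilson 95% interval | 47.0% to 75.8% |
| Jeffreys 95% interval | 47.1% to 76.2% |
| Wald 95% interval | 47.5% to 77.5% |
| Mid-p, two-sided | 0.117 |
| Normal approximation, two-sided | 0.114 |
| Normal approximation, continuity-corrected | 0.155 |
| Exact, one-sided | 0.077 |

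Every interval includes 50% and no p-value reaches 0.05. The absence of a pre-named method therefore left no room for the choice among these pooled methods to change the reading.

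**5. Does order matter?** The pooled calculation ignores whether the preferred injection came first or second. The documents do not give the number of patients per sequence, so the following rests on assumed sequence sizes. Fisher's test of sequence against preferred position, over all splits that total 25 for Dentapen, gives:
- 20 and 20 patients per sequence: p from 0.047 to 0.205, with only the most extreme splits (20 and 5 choosing Dentapen in the two sequences) below 0.05
- 24 and 16: p from 0.006 to 0.553

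With balanced sequences the reading would almost certainly stand. With marked imbalance it could move, and the documents do not allow that to be settled.

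**6. Is preference really treated differently from the other outcomes?** Less than it seems. Preference compares the two devices. The intervals in Table 3 are for before minus after within each device and overall; none is for Dentapen against Vibraject. The mean rises are 1.525 and 0.275, and their difference, 1.525 − 0.275 = 1.25, has no interval or p-value. VAS has a p-value for the device comparison but no interval. Preference is therefore not the only outcome whose device comparison lacks a measure of uncertainty.

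**7. What does the text claim?** That the larger number chose Dentapen. This is literally true of 25 against 15. It does not say that the difference is significant, nor that Dentapen is preferred in general.

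**The case for a change.** The strongest case for acting is that the omission is real and the repair nearly free. The document's own standard for a real difference is p of 0.05 or less. The preference split does not meet it, and the text does not say so, although the VAS text does for its own result. One sentence with an exact interval, marked post hoc, would prevent over-reading and would need only data already held.

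Much of this stands. The outcome is stated, no analysis is named, and the text has no interval. Adding one would be good reporting practice, and its wording should be that the pooled result is inconclusive, which is different from no preference.

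Three points limit it. First, the addition would correct nothing that is stated: the counts are right and no inference is drawn from them. Second, referring to the primary statistical tests leaves room for other outcomes to be described without a test, which is a reasonable way to treat a question with no stated hypothesis. Third, there is no ground for making the pooled interval the one governing analysis and ruling out any other. Preference was recorded by position, so an analysis by order is a legitimate alternative, and the assumed sequence sizes above show that the two can differ.

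**Conclusion.** No change to the plan follows. This is missing detail in a descriptively reported outcome, and an analyst or reader fills it sensibly from the counts given. The size is known: 62.5%, exact 95% interval 45.8% to 77.3%, two-sided p = 0.154, two patients short of the 27 needed for 0.05. The pooled split is compatible with a slight preference for Vibraject, with no preference, and with a strong preference for Dentapen, and nothing in the Results text says otherwise.

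This rests on three assumptions: a two-sided reading of the 0.05 threshold; independent answers from 40 patients, all forced to choose; and order that is either balanced or without effect, which the documents do not allow to be checked. It also concerns the text alone, because an interval or test shown in Figure 4 cannot be excluded. The conclusion would differ if the document called the preference difference significant or based a claim of Dentapen's superiority on it; it does neither.

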- Pregnant or nursing women, this is to avoid any potential risks to their health or that of their infants.
- Individuals who were actively taking drugs that could alter pain perception or anxiety levels, such as nonsteroidal anti-inflammatory drugs, opioids, or antidepressants. This was to ensure that the study's findings on pain perception were not influenced by external substances
- Individuals with heavy alcohol consumption. .
- Patients with active pathologies at the injection site, this is to avoid complications and to ensure the accuracy of the study's results.
- Individuals who could not commit to the study's schedule or were unable to give informed consent. This ensured that all participants were fully aware of and agreeable to the study's procedures and requirements.
- Patients who required intravenous sedation for their dental procedures.

Sample Size

The study was designed with a carefully considered sample size to ensure statistical significance and reliability of the results. The sample size for the study was determined utilizing the G-power calculator, resulting in a decision to allocate 40 participants to each of the two groups, with each participant receiving two different injections, thereby evaluating 80 sites in total. This approach allowed for a comprehensive comparison between the two injection types, as each patient served as their control.

Study Design

The study commenced with an initial assessment to determine patient eligibility. Once eligibility was confirmed, the patient was scheduled for their first injection, during which their baseline heart rate was measured before any procedures. Following this, the patient received the first local anaesthesia injection using one of the two methods being compared in the study. After the injection was administered, the patient's heart rate was measured again to record any changes that may have occurred due to the injection then the patient will be asked to evaluate pain intensity with Visual Analogue Scale.

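### The Overall heart-rate row of Table 3 treats 80 injections from 40 patients as independent, so its SE, CI and p-value use the wrong unit of analysis (low priority)

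*Combined protocol and SAP*

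**What the plan says.** The Study Design section states: "This study design is a split mouth clinical trial which allowed for a within-subjects comparison". Step III of Steps of the Experiment adds that "each patient was given local anaesthesia twice, once with the Dentapen system (ramp-up mode) and once with Vibraject". The Sample Size section describes the allocation "with each participant receiving two different injections, thereby evaluating 80 sites in total" and gives the rationale "as each patient served as their control". Table 1 has N=40.

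The Statistical Analysis section assigns the paired t-test to heart rate, to detect a "statistically significant change in heart rate following the administration of local anaesthesia". It sets significance at 0.05 or less and says nothing about how two changes from one patient would be combined.

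In Results, Table 2 prints N=80 for the Overall rows and N=40 for each device. Table 3 then gives an Overall before-after comparison: mean -0.900, SD 4.18133, SE 0.46749, 95% CI -1.83051 to 0.03051, t -1.925, p=0.058. Its footnote reads "P-value has been calculated using paired sample t-test". The text reports that "no significant differences were observed in the mean heart rate measurements between the overall and Vibraject before and after injection".

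**The concern.** A paired t-test on before-after changes deals with the pairing within one injection. It does not deal with each patient supplying two such changes. If those two changes are correlated, 80 of them do not carry the information of 80 independent patients, and SD/sqrt(80) with 79 df is not the right standard error for the pooled mean.

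What is at stake is narrow: the Overall half of one Results sentence, with its CI and p-value. The printed p=0.058 does lie close to the 0.05 threshold, so it cannot be assumed without checking that the choice of unit is harmless. Asking a pooled before-after question is compatible with the Statistical Analysis section. The concern is the unit of analysis only.

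**Working it through.** **Inputs (Results, Table 3, before minus after).** Dentapen: mean -1.525, SD 3.56613. Vibraject: mean -0.275, SD 4.67940. There are 40 changes per device (Table 2) from 40 patients (Table 1). Sidedness is not stated; two-sided tests reproduce the printed p-values.

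**Step 1: reproduce the printed row.** The overall mean is (-1.525 - 0.275)/2 = -0.900, so each device mean lies 0.625 from it. Stacking the two device rows gives

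SD = sqrt{[39 × (3.56613² + 4.67940²) + 80 × 0.625²]/79} = 4.18133

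SE = 4.18133/sqrt(80) = 0.46749; t = -0.900/0.46749 = -1.925; with 79 df, p = 0.0578 and CI -1.8305 to 0.0305.

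Every figure matches the table. With the same SD and n=40, SE would be 0.661 and p 0.18, which does not match. The row therefore treats 80 changes as independent.

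**Step 2: check the device rows.** With n=40 and 39 df, Dentapen gives SE 0.564 and p=0.010, and Vibraject gives SE 0.740 and p=0.712, as printed. Each patient enters each of these rows once, so they do not have the fault.

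**Step 3: redo the Overall row with the patient as the unit.** Average the two changes within each patient (n=40, 39 df, t quantile 2.0227). The mean stays at -0.900, and

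SE = sqrt[(3.56613² + 4.67940² + 2r × 3.56613 × 4.67940)/(4 × 40)] = sqrt[(34.614 + 33.375r)/160]

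Here r is the within-patient correlation of the two changes. The documents do not report it, and it cannot be recovered from the printed SDs, so it is varied as an assumption.

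| Assumed r | SE | 95% CI | CI width against printed 1.861 | p |
|---|---|---|---|---|
| -0.2 | 0.418 | -1.75 to -0.05 | 9% narrower | 0.0375 |
| -0.1 | 0.442 | -1.79 to -0.01 | 4% narrower | 0.0486 |
| 0 | 0.465 | -1.84 to 0.04 | 1% wider | 0.060 |
| 0.1 | 0.487 | -1.89 to 0.09 | 6% wider | 0.072 |
| 0.3 | 0.528 | -1.97 to 0.17 | 15% wider | 0.096 |
| 0.5 | 0.566 | -2.05 to 0.25 | 23% wider | 0.120 |
| 0.7 | 0.602 | -2.12 to 0.32 | 31% wider | 0.143 |
| 1 | 0.652 | -2.22 to 0.42 | 42% wider | 0.175 |

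**Step 4: find the crossing points.** p=0.05 needs SE = 0.900/2.0227 = 0.44495, so r = (160 × 0.44495² - 34.614)/33.375 = -0.088. The patient-level CI has the printed width when SE = 1.861/(2 × 2.0227) = 0.4600, which gives r = -0.023; above that it is wider than printed. The SE itself equals the printed 0.46749 at r = 0.011.

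**The case against.** The strongest reply is that no wrong conclusion has been shown. At r=0 the patient-level result (SE 0.465, p=0.060) is almost the printed one (SE 0.467, p=0.058), and the reading stays non-significant for every r from 0 to 1. The trial compares two devices, and a pooled before-after change says nothing about that comparison. The per-injection unit was also not hidden: Table 2 prints N=80 and the Sample Size section speaks of 80 sites.

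Most of this stands and sets the priority. Disclosing 80 sites, however, does not justify treating them as independent, and a CI and p-value printed and interpreted in the text should rest on the right unit.

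A second objection is that the sign of r is unknown. The documents offer no evidence for a negative r and none for a positive one, so it should not be claimed that recomputation will probably widen the CI. This is accepted. Even if the true correlation were zero, a sample r from 40 patients has SD of about 1/sqrt(39) = 0.160. By normal theory it would fall below -0.023 about 44% of the time and below -0.088 about 29% of the time. The direction is therefore open, which is a reason to compute r from the data rather than assume the row is harmless.

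**Conclusion.** The concern holds, at low priority. It is certain that the Overall row is computed on 80 stacked changes, and the design makes these 40 within-patient pairs. Its SE, CI and p=0.058 therefore rest on an independence assumption that the split-mouth design does not support.

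The size of the error is not known, because r is not reported. Over r from 0 to 1 the correct CI would be between 1% and 42% wider than printed, and p would lie between 0.060 and 0.175. The statement of no significant overall change would have to be reversed only if r were below about -0.09.

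The device-specific rows, including the only significant heart-rate result (Dentapen, p=0.010), are not touched by this fault. The point bears on this one row only and says nothing either way about the comparison between devices.

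**What to change.** Recompute the Overall row of Table 3 as a one-sample t-test on the 40 per-patient mean changes (39 df), report r, and revise the Overall clause in the Results text to match. This test accommodates a correlation of either sign, so no model is needed. If a model is preferred, it must allow negative within-patient covariance, for example an unstructured 2×2 covariance. An ordinary random-intercept model cannot represent a negative r, the only case that would change the conclusion.

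The alternative is to delete the Overall row and its clause. Recomputation is preferable because deletion drops a borderline result that has already been reported, and with it the pooled estimate.

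The cost is a short re-run on existing data and an edit to one row and one clause. The CI will be wider than printed if r is above about -0.02 and narrower if it is below. The text on overall significance needs reversing only if r is below about -0.09.

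### Table 4 compares pain in a split-mouth trial with a p-value footnoted as Mann-Whitney and no within-patient difference or interval, so the precision of the comparison cannot be recovered

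*Combined protocol and SAP*

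**What the plan says.** The Study Design section states: "This study design is a split mouth clinical trial which allowed for a within-subjects comparison". The Sample Size section describes 40 participants, "with each participant receiving two different injections, thereby evaluating 80 sites in total". The Statistical Analysis section assigns pain to the Wilcoxon test, presents it as a test for related or matched samples, and says "it was employed to evaluate the differences in pain scores between the two different injection techniques on the same patients". The decision rule is "A p-value of 0.05 or less was considered statistically significant", and a result below that threshold is read as "suggesting a real difference between the two techniques that is not due to random variation". No estimate or interval is specified for any outcome.

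In Results, Table 4 lists mean, N, SD and SE for each device and for the 80 sites pooled, with one p-value of 0.105. Its footnote attributes that p-value to a Mann-Whitney test, which treats the two sets of scores as independent samples. The text says "The mean score of Vibraject (2.175) was observed higher than that of Dentapen (1.550") and then "However, the results yielded an insignificant difference (p=0.105"). Table 3 presents heart rate differently: it gives paired differences with SD, SE and a column headed "95% Confidence Interval of the Difference".

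**The concern.** Two things are wrong together. The p-value is labelled as coming from an unpaired test, although the methods section describes a paired one. And the table carries no measure of how precisely the within-patient difference is known. The per-device SEs describe variation between patients on one device. They do not give the precision of a comparison in which each patient is their own control.

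At stake is what the trial can say about pain. A bare verdict of non-significance does not tell the reader which differences the data still allow in either direction. If the two scores are positively correlated within patients, the unpaired analysis is also less sensitive than the one described, so the verdict itself may depend on the departure.

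**Working it through.** **Inputs.** Table 4: Dentapen mean 1.550, SD 1.467; Vibraject mean 2.175, SD 1.693; N = 40 each. I assume 40 complete pairs and a two-sided 5% level (sidedness is not stated). The within-patient correlation r of the two pain scores is not in the documents and is varied as an assumption.

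**1. Reproduce Table 4.** 1.467/√40 = 0.232 and 1.693/√40 = 0.268, as printed. The overall mean is (1.550 + 2.175)/2 = 1.8625, printed as 1.863. The overall SE is 1.605/√80 = 0.179. The descriptive figures are consistent.

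**2. The printed p-value.** A Mann-Whitney p needs the individual scores, so 0.105 cannot be reproduced. As a plausibility check only, an unpaired t-test from the same summaries gives 0.625/0.354 = 1.76 and p = 0.082 on 78 df. A value of 0.105 is therefore plausible for an unpaired rank test. A paired t-test would give 0.105 only at r of about -0.13.

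**3. Point difference.** Dentapen minus Vibraject = 1.550 - 2.175 = -0.625; negative values favour Dentapen.

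**4. What the printed SEs imply.** √(0.232² + 0.268²) = 0.354. This is the SE of the paired difference only when r = 0.

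**5. Paired interval for assumed r.** SD of the difference = √(1.467² + 1.693² - 2r × 1.467 × 1.693) = √(5.018 - 4.967r). SE = SD/√40. 95% CI = -0.625 ± 2.0227 × SE (39 df).

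| Assumed r | SD of difference | SE | 95% CI | Paired t, p |
|---|---|---|---|---|
| -0.2 | 2.452 | 0.388 | -1.41 to +0.16 | 0.115 |
| 0 | 2.240 | 0.354 | -1.34 to +0.09 | 0.086 |
| 0.3 | 1.878 | 0.297 | -1.23 to -0.02 | 0.042 |
| 0.5 | 1.592 | 0.252 | -1.13 to -0.12 | 0.017 |

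**6. Where zero leaves the interval.** This needs SD = 0.625 × √40/2.0227 = 1.954, so r = (5.018 - 1.954²)/4.967, or about 0.24.

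The correlations between heart rate before and after an injection that Tables 2 and 3 imply say nothing about r between devices for pain, and I did not use them.

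**The case against.** The strongest reply is that this is a reporting gap of limited weight. Table 4 does print means, Ns and SDs, the text states the direction, and the difference follows by subtraction. That stands: only the precision is missing. A reader might infer that the p ≤ 0.05 rule left the trial unable to produce an interval. Table 3 contradicts this, since intervals appear there without having been planned. The comparison with Table 3 is itself limited, because it reports before-after change within each device, not a between-device difference. The documents also name no single primary outcome; the heart-rate and pain tests are both listed as primary.

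A second reply is that the intervals above rest on an unknown r. That also stands. A negative r is possible: with randomised order, a difference between first and second injections pushes the two device scores in opposite directions within patients. And the t-based intervals concern means, whereas the methods section prefers a rank test.

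The footnote might be only a labelling slip, with the signed-rank test in fact run. Summary data cannot settle this. If so, the p-value would stand, but the paired estimate and interval would still be absent.

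**Conclusion.** The point holds as a combined defect: the p-value for pain is attributed to a test that ignores the pairing, and no within-patient estimate of precision is given. Over assumed r from -0.2 to 0.5, the lower limit moves from -1.41 to -1.13 and the upper from +0.16 to -0.12. At r = 0.5 the SE implied by the printed figures is 41% too large (0.354/0.252 = 1.41).

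Two stronger readings are tempting, and the documents support neither. A reader might infer that the correct analysis would have been significant in favour of Dentapen. That depends on whether r exceeds about 0.24 (for a t-test), r is not reported, and the signed-rank test may behave differently. A reader might also infer that the report claims equal pain with the two devices. It does not: it states that the Vibraject mean was higher and then reports non-significance. Nor can any of these intervals be called clinically relevant or irrelevant, because no clinically important difference is defined. The figures illustrate the range; the actual interval needs the individual pairs.

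**What to change.** 1. Analyse the 40 pairs with the Wilcoxon signed-rank test, as the Statistical Analysis section describes, and correct the Table 4 footnote to match.
2. State in Statistical Analysis that the Hodges-Lehmann estimate of the within-patient difference (Dentapen minus Vibraject), with its 95% CI, governs the conclusion on pain. State also how ties and zero differences are handled. The printed means give totals of 40 × 1.550 = 62 and 40 × 2.175 = 87, consistent with whole-number scores, so ties are likely.
3. Add a descriptive paired-difference row to Table 4: mean, SD, SE and 95% CI, in the layout of Table 3.
4. Replace the sentence reporting p = 0.105 with the paired estimate, its interval and the paired p-value. Do not decide in advance which way it will fall.

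The cost is a short extra analysis of existing data, one table row and a few sentences. The downside is that the reported conclusion on pain may change.
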